12.2.1 Adverse Events

All adverse events occurring during the study will be recorded and classified on the basis of MedDRA terminology. Descriptions of AEs will include the date of onset, the date the AE

ended, the severity of the AE, the relationship to study medication, the action taken regarding study medication usage, the action taken regarding to treat the AE, and the outcome. All reported treatment-emergent AEs (TEAEs) will be summarized by the number of Subjects reporting AEs, system organ class, severity, seriousness, and relationship to study medication. TEAEs are those AEs with an onset on or after the date of the first study drug application.

Adverse events will be summarized by treatment group and severity. Each subject will be counted only once within a system organ class or a preferred term by using the adverse events with the highest severity within each category.

Adverse events will be summarized by treatment group and relationship to study medication. Each subject will be counted only once within a system organ class or a preferred term by using the adverse events with the greatest relationship within each category.

Comparisons among treatment groups will be made by tabulating the frequency of subjects with one or more AEs (classified into MedDRA terms) during the study. The Fisher's Exact test will be used to compare the proportion of subjects in each treatment group who report any adverse event at a significance level of 0.05. The specific system organ classes and preferred terms analyzed will be those that are reported by at least one percent of the subjects in any treatment group.

All information pertaining to AEs noted during the study will be listed by subject, detailing verbatim given by the investigator, preferred term, system organ class, start date, stop date, severity, actions taken, and drug relatedness. The AE onset will also be shown relative (in number of days) to the day of initial dose of the randomized study medication.

Serious adverse events (SAEs) will be tabulated by subject within treatment groups.

In addition, a list of subjects who discontinued from the study and a list of subjects who experienced SAEs will also be provided.

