Photographs (select sites only)		X			X
Cutaneous Safety Evaluation		X	X	X	X
Tolerability Evaluation		X	X	X	X
Randomization in IWRS (obtain kit #)		X	X	X	
Administer Subject Instructions (Appendix 17.1)		X			
Dispense Study Drug ⁵		X	X	X	
Weigh Study Drug to the nearest 0.1gram		X	X	X	X
Study Drug applied at investigational center		X			
Study Drug Collected			X	X	X
Subject Diary Calendar dispensed		X	X	X	
Subject Compliance Reviewed / Diary			X	X	X
Adverse Events	X	X	X	X	X
Concomitant Therapy and Prohibited Therapies Review	X	X	X	X	X
End of Study					X

¹ If no washout is needed, Visits 1 and 2 may occur on the same day. If a washout is needed, Visit 2 must occur after the appropriate washout period.

² All visit dates are in reference to baseline, e.g., Visit 4 occurs 8 weeks +/- 3 days after baseline visit.

³ All Week 12 procedures should be completed for all subjects who terminate early.

⁴ The Week 2 SSA will be sent home with the subject during the baseline visit (Visit 2) with instructions to complete it at two weeks and return it at the Week 4 visit. The site should call the subject at Week 2 to remind them to take the Week 2 SSA.

⁵ Dispense one tube of test material at the Baseline, Week 4 and Week 8 visits.

8 Selection and Withdrawal of Subjects

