12. The study coordinator or designee will instruct the subject on the proper application procedure for the study drug per Section 10.1.3, and will provide written subject use instructions to the subject (Appendix 17.1). For the first application, the subject will apply the study drug at the investigational center under the direction of the study coordinator or designee. The study drug should be applied after all clinical assessments. The study coordinator or designee will instruct the subjects to apply the study drug once daily at home.
13. Record any AEs or changes in AEs since the screening visit and/or reported spontaneously by the subject.
14. *Selected Sites only* - Obtain representative photographs of the face.
15. Schedule the next study visit at Week 4 (Day 28 ± 3 days). Remind the subject to not apply test medication on day of next study visit, prior to the clinic visit.

11.1.3 Visit 3 and 4: Week 4 (Day 28 ± 3 Days) and Week 8 (Day 56 ± 3 Days) Visits

The following procedures will be conducted at this visit (if a subject terminates early, all final visit (Week 12/Final Visit) procedures must be performed):

1. The take-home Week 2 SSA will be collected during the Week 4 study visit.
2. The Week 4 or Week 8 SSA will be conducted and collected.
3. The Evaluator will perform the efficacy evaluations including the Evaluator's Global Severity Score (EGSS), inflammatory lesion counts and non-inflammatory lesion counts. The EGSS is performed prior to the lesion counting. Every effort should be made for the same qualified and validated evaluator to perform the efficacy evaluations at all visits from Baseline to Week 12 for the same subject.
4. The Evaluator will perform Cutaneous Safety and Tolerability Evaluations.
5. Record changes in any concomitant medications since the previous visit under Prior and Concomitant Medications or Therapies. Check for prior and concomitant therapies as per Section 9.4.
6. Record any new AEs reported spontaneously by the subject or changes in any ongoing AEs.

7. Perform a Urine Pregnancy Test for all females that are pre-menses and females of childbearing potential. The urine pregnancy tests will be supplied by the CRO.

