11.4 Adverse Events

11.4.1 Definition of Adverse Event

An AE is any untoward medical occurrence in a patient or clinical investigation subject administered a medicinal product and which does not necessarily have a causal relationship with the study drug. AEs include any unfavorable and unintended illness, sign, symptom, clinically significant laboratory test abnormality, or disease temporally associated with the use of a medicinal product that has appeared or worsened during the course of the clinical trial, regardless of causal relationship to the study drug(s) under study. AEs include any illness, sign, symptom, or out-of-range and clinically significant laboratory finding that has appeared or worsened during the course of the clinical trial, regardless of causal relationship to the study. The collection of non-serious AEs and serious adverse events (SAEs) will begin following the subject's completion of the consent process to participate in the study.

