11.4.2 Documenting Adverse Experiences

It is the responsibility of the investigator to document all AEs that occur during the course of the study. The AEs should be documented as a single medical diagnosis. When this is not possible, the AE should be documented in terms of signs and/or symptoms observed by the investigator or reported by the subject at each study visit. Each AE which appears to be independent of any prior event will be reported separately.

All AEs occurring after the subject signs the informed consent through the last study visit must be reported, regardless of whether or not the AEs are considered drug-related. All AEs, whether in response to a query, observed by the study site personnel, or reported spontaneously by the subject, will be recorded. Any AEs deemed related to treatment reported or observed at the final study/treatment visit will be followed until stabilization or resolution (or up to 30 days after final study visit).

At each visit during the study, the subject will be assessed for the occurrence of new and ongoing AEs. Cutaneous tolerability signs and symptoms that result in the subject's requiring a concomitant therapy or discontinuation from the study will be reported as an AE. The following data will be collected on all AEs and recorded on the appropriate CRF:

- Event name (diagnosis preferred, if unknown, record the signs/symptoms)
- Onset date and end date
- Maximum intensity (severity)
- Seriousness
- Action taken regarding study drug
- Corrective treatment, if given

- Outcome

In addition, the investigator's assessment of causality will be recorded.

Vital sign abnormalities are to be recorded as AEs only if they are clinically significant (for example: are symptomatic, requiring corrective treatment, leading to discontinuation or fulfilling a seriousness criterion).

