11.4.4 Assessment of Severity

The severity assigned to an AE should be determined by the maximum severity of the AE. The categories described below should be used to estimate the severity of AEs:

- Mild: Transient or mild discomfort; no limitation in activity; no medical intervention/therapy required

- **Moderate:** Mild to moderate limitation in activity; some assistance may be needed; no or minimal medical intervention/therapy required
- **Severe:** Marked limitation in activity; some assistance usually required; medical intervention/therapy required; hospitalization or prolongation of current hospitalization possible; may be incapacitating or life threatening

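### The TEAE rule in 12.2.1 uses onset date only, so an AE open before first dose that worsens on drug would be left out of the TEAE summary

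*Combined protocol and SAP*

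**What the plan says.** The current protocol (Amendment 3), Section 12.2.1, gives one criterion: "TEAEs are those AEs with an onset on or after the date of the first study drug application". The protocol before amendment has the same sentence in its own 12.2.1, and none of the three summaries of changes alters it. The sentence before it in 12.2.1 says which summaries are built on TEAEs: numbers of subjects, system organ class, severity, seriousness and relationship.

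The AE definition in 11.4.1 is wider. It covers anything "that has appeared or worsened during the course of the clinical trial". Collection starts well before dosing: 11.4.1 says that it "will begin following the subject's completion of the consent process", and 11.4.2 adds that "All AEs occurring after the subject signs the informed consent through the last study visit must be reported".

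Three recording rules matter here:
- Section 11.4.2: "Each AE which appears to be independent of any prior event will be reported separately".
- Section 11.1.3, for Weeks 4 and 8 (repeated in 11.1.4 for Week 12): "Record any new AEs reported spontaneously by the subject or changes in any ongoing AEs".
- Section 11.4.4: "The severity assigned to an AE should be determined by the maximum severity of the AE".

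**The concern.** A common way to define a treatment-emergent event is to include both events that start after first dose and events present before it that get worse. The rule in 12.2.1 keeps the first half and drops the second, although the protocol's own AE definition contains both. A complaint that is mild during screening or washout and becomes severe after treatment starts is something a between-group safety summary should show. If it keeps its pre-dose onset date, it does not count as treatment-emergent, however severe it becomes and even if the investigator judges it related. At stake is the completeness of the TEAE summary. No efficacy conclusion depends on it.

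**Working it through.** There is no figure to reproduce and no formula to apply. The check is whether the stated rules, followed together, exclude the event.

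**1. Can an AE be open before first application?** Yes. Collection runs from consent (11.4.1, 11.4.2), the schedule in Table 1 marks AEs at both Screening and Baseline, and the first application takes place at the Baseline visit (11.1.2).

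**2. How long is the exposed period?** It is the date of first application minus the date of consent.
- No washout: "If no washout is needed, Visits 1 and 2 may occur on the same day" (Table 1, footnote 1). The difference is then 0 days. The TEAE rule compares dates, so an AE with onset on Day 0 counts even if it began before the application. These subjects are not exposed to the problem.
- Washout needed: Baseline must follow it. The required drug-free intervals in 8.2 are 1 to 4 weeks, or 6 months for systemic retinoids. The exposed period is whatever part of the interval remains after consent, which the documents do not give.

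**3. What happens to the record when the AE worsens on drug?**

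| Rule | Consequence |
|---|---|
| 11.4.2: a separate report is for an event independent of any prior one | Worsening of the same complaint is not independent, so no new record is called for |
| 11.1.3 and 11.1.4: changes to ongoing AEs are recorded | Worsening updates the existing record |
| 11.4.4: severity is the maximum for the AE | The record ends with one severity, the worst reached |
| 11.4.2: onset date, end date and maximum intensity are among the items collected | The listed items include no date for a change in severity |

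The most natural result is one AE with a pre-dose onset date and an on-treatment maximum severity.

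**4. Does 12.2.1 count it?** The onset date precedes first application, so it is not a TEAE.

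**5. Where does it still appear?**
- The by-subject listing covers all AEs and shows onset relative to first dose.
- The separate severity and relationship summaries and the Fisher comparison are worded in terms of AEs generally. Section 12.2.1 does not say whether they are restricted to TEAEs. If they are, they lose the event too. If not, they keep it, but they also count pre-dose AEs that never worsened, and they may not agree with the TEAE summary.
- Scaling, erythema, hypo- and hyper-pigmentation, itching, burning and stinging are each graded 0 to 3 (11.3.1, 11.3.2) and tabulated by arm at Baseline and Weeks 4, 8 and 12 (12.2). Worsening of these signs is visible whatever the AE onset date.

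**6. How many events?** This cannot be derived. It would need the proportion of subjects who need washout, the AE rate between consent and first dose, and the proportion of those AEs that worsen on drug. The documents give none of these.

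**The case against.** The strongest counter-argument is that no section states that a worsened AE keeps its onset date. Because 11.4.1 makes worsening itself an AE, an investigator could enter the aggravation as a new AE dated from the worsening, and it would then qualify. That reading is possible, but it runs against the three recording rules above. If sites differ in which they follow, the TEAE count depends on site habit.

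Second, 11.3.1 requires a tolerability sign or symptom that leads to concomitant therapy, interruption or discontinuation to be reported as an AE. For a symptom not already an AE, this gives an on-treatment onset, and the same holds for a medical-history condition that first worsens on drug. This stands, and it narrows the gap to AEs already open before first application. For those, 11.3.1 does not call for a new onset date.

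Third, the visit-wise scores cover much of the local picture. This also stands in part. They do not grade dryness, which Section 5 names as a known side effect of topical retinoids, and they carry no relatedness, seriousness or action taken.

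Fourth, Section 12 announces a separate SAP, which might define TEAEs differently. No other definition is in the supplied text, and the protocol sentence would still need to agree with it.

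A reader might go further and infer that the safety reporting as a whole undercounts drug-aggravated events. The documents do not support that: only one summary sentence in 12.2.1 is worded as TEAE, and the listing keeps every event. Nor should the washout lengths be read as the length of the exposed period. They are required drug-free intervals, and part or all of one may have passed before consent.

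**Conclusion.** The point holds as a defect in a stated rule. As written, and with the protocol's recording rules followed as they most naturally read, an AE open before first application that worsens on drug is omitted from the TEAE summary. This rests on the worsening being recorded as a change to the existing AE, and on the SAP not redefining the term.

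The effect is small, probably a few events, and its direction is an undercount in the TEAE summary only. It is nil for subjects screened and dosed on the same day. It might be inferred that the loss falls mostly on the active arm. That is plausible, since Section 5 describes topical retinoids as irritant and pre-dose AEs themselves should be balanced by randomization. The documents give no rate of aggravation by arm, however, so the size of any imbalance cannot be stated. The change is worth making because it is cheap.

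**What to change.** Three changes, to be carried into the SAP:

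1. In 12.2.1, define a TEAE as an AE with onset on or after the first application, or with onset before it and an increase in severity on or after it.
2. In 11.4.2, say how worsening of an ongoing AE is recorded: either a new record dated from the worsening or a dated severity change on the existing one. The first change cannot be applied reliably without this, because a single undated maximum severity does not show whether the increase came before or after first dose.
3. In 12.2.1, state for each table, and for the Fisher comparison, whether it uses TEAEs or all AEs.

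The cost is one clause in the definition, a small addition to AE recording and site instructions, and a slightly longer derivation. No visit, assessment or change in sample size is needed.

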12.2.2 Safety Laboratory Tests

Changes from baseline in safety laboratory values will be summarized with descriptive statistics at Week 12. Shift tables will be presented for changes in safety laboratory values. Normal ranges established by the central laboratory will be used to determine the shifts. A listing of all out-of-range laboratory test results at any assessment time point will also be provided. Determination of clinical significance for all out-of-range laboratory values will be made by each investigator and included in the listing. In addition, a listing of all clinically significant laboratory test results will be provided.

12.2.3 Vital Sign Measurements

Changes from Baseline in vital sign measurements will be summarized with descriptive statistics for each treatment group at all applicable study visits.

12.2.4 Concomitant Medications

All previous therapies and concomitant medications will be classified based on terminology from the WHO Drug Dictionary. Previous therapies and concomitant medications data will be presented in data listings.

12.2.5 Subject Self-Assessments

Subjects will be asked to complete three questionnaires during the study: the Subject Self Assessment scale, the Patient Satisfaction Survey and the Acne-Specific Quality of Life Questionnaire (Appendices 17.3, 17.4 and 17.5). Descriptive statistics will be used to summarize the data reported for each questionnaire. No Inferential analyses will be conducted.

12.3 Subject Disposition

A tabulation of subject disposition will be provided. The tabulation will include the numbers of subjects who enter the study, complete the study, and discontinue the study. The reasons for discontinuation will be included.

12.4 Demographics and Baseline Characteristics

Subject demographic and baseline characteristics will be summarized by treatment group for both the ITT population and the PP population. For continuous variables (e.g. age) comparisons among the two treatment groups will be conducted using a two-way analysis of variance (ANOVA) with factors of treatment group and analysis center. Ethnicity and race will be analyzed with a Cochran-Mantel-Haenszel test stratified by analysis center. Past and current medical conditions, as well as history of disease will not be compared statistically.

12.5 Protocol Deviations

All protocol deviations will be reported to the sponsor and recorded throughout the study. A listing of protocol deviations will be included in the final study report.

12.6 Compliance

No formal evaluations of compliance are planned.

12.7 Interim Analyses

No interim analyses are planned.

12.8 Additional Statistical Considerations

12.8.1 Analysis Populations

Approximately 800 subjects at least 9 years of age and older with moderate or severe acne (a score of 3 or 4 [moderate to severe] on the EGSS scale) will be enrolled and randomized in the study. With a 1:1 randomization ratio, it is anticipated that:

- 400 subjects will be randomized to receive IDP-121 Lotion, once daily application
- 400 subjects will be randomized to receive IDP-121 Vehicle Lotion, once daily application

The ITT population will consist of all randomized subjects who received study medication. The safety population will be comprised of all randomized subjects who are presumed to have used the study medication at least once and who provide at least one post-baseline evaluation.

An intent-to-treat (ITT) analysis will be conducted on all study subjects. A per-protocol (PP) analysis will also be conducted. Subjects will be eligible for the PP analysis if they complete the 12-week evaluation without noteworthy study protocol violations (i.e., any subject or investigator activity that could have possibly interfered with the therapeutic administration of the treatment or the precise evaluation of treatment efficacy). The PP population will include subjects in the safety population who do not meet any of the following criteria:

- Failed any of the inclusion/exclusion criteria;
- Have taken any interfering concomitant medications;
- Did not attend the Week 12 visit, with the exception of a discontinuation from the study due to an adverse event related to study treatment or documented lack of treatment effect;
- Missed both the week 4 and week 8 visits;
- Have not been compliant with the dosing regimen (i.e. Subjects may not miss more than five consecutive days of dosing and must take 80-120% of expected doses. The number of expected doses will be determined for each subject based on the length of their participation in the study);
- Out of visit window at the 12-week visit.

Prior to breaking the blind, other additional criteria may be added to the list to accommodate for unforeseen events that occurred during the conduct of the trial that result in noteworthy study protocol violations.

The safety population will be comprised of all randomized subjects who are presumed to have used the study medication at least once and who provide at least one post-baseline evaluation.

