The safety population will be comprised of all randomized subjects who are presumed to have used the study medication at least once and who provide at least one post-baseline evaluation. A per-protocol (PP) analysis will also be conducted. Subjects will be eligible for the PP analysis if they complete the 12-week evaluation without noteworthy study protocol violations (i.e., any Subject or investigator activity that could have possibly interfered with the therapeutic administration of the treatment or the precise evaluation of treatment efficacy). The PP population will include subjects in the ITT population who do not meet any of the following criteria:

- Failed any of the inclusion/exclusion criteria;
- Have taken any interfering concomitant medications;
- Did not attend the Week 12 visit, with the exception of a discontinuation from the study due to an adverse event related to study treatment or documented lack of treatment effect;
- Missed both the week 4 and week 8 visits;
- Have not been compliant with the dosing regimen (i.e. Subjects may not miss more than five consecutive days of dosing and must take 80-120% of expected doses. The number of expected doses will be determined for each subjects based on the length of their participation in the study);
- Out of visit window at the 12-week visit

Prior to breaking the blind, other additional criteria may be added to the list to accommodate for unforeseen events that occurred during the conduct of the trial that result in noteworthy study protocol violations.

Approximately eight hundred (800) subjects will be randomized to the following treatment groups:

- 400 Subjects to IDP-121 Lotion, once-daily application
- 400 Subjects to IDP-121 Vehicle Lotion, once-daily application

Efficacy:

Primary:

Co-primary efficacy analyses of the absolute change in inflammatory and in non-inflammatory lesions will be conducted on the ITT population. The pre-specified time point will be Week 12. Descriptive statistics will be presented by treatment group for inflammatory and for non-inflammatory lesions as well as the absolute change in inflammatory and in non-inflammatory lesions. All of the testing relating to the analysis of inflammatory and non-inflammatory lesions will use the methods introduced in Section 12.

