The co-primary analysis of the dichotomized EGSS (success being at least a 2 grade improvement and achieving Clear or Almost Clear) for the ITT population will be based on the logistic regression test stratified by analysis center.

Secondary:

Mean percent change in inflammatory and non-inflammatory lesion counts from baseline to Week 12.

Supportive:

Additional supportive efficacy endpoints (including mean percent change in inflammatory and non-inflammatory lesions counts from baseline at Weeks 4 and 8, as well as proportion of subjects with at least a two grade improvement in the Evaluator's Global Severity Score from baseline at Weeks 4, 8 and 12) will be conducted, as noted above.

Safety Evaluation:

All subjects who receive medication and provide at least one post-baseline evaluation will constitute the safety population.

Safety will be evaluated by tabulations of adverse events (AEs), Cutaneous Tolerability Evaluations. Cutaneous Safety Evaluation scores (erythema, scaling, and hypo/hyper-pigmentation) and Tolerability (itching, burning, and stinging) will be presented with descriptive statistics at Baseline and at Weeks 4, 8, and 12 for each treatment group. Frequencies and percentages for each outcome category will be included in these statistics. Mean values will be presented graphically by week and treatment group.

Vital signs and an abbreviated physical exam, and safety labs will be conducted on all subjects at specified visits. For females of child-bearing potential (FOCBP), urine pregnancy testing will occur at specified visits. Changes from baseline in safety laboratory values and vital sign measurements will be summarized with descriptive statistics for each treatment group at all applicable study visits. Shift tables will be presented for changes in safety laboratory values to summarize laboratory test results collected at Baseline and Week 12. Normal ranges established by the central laboratory will be used to determine the shifts. A listing of all out-of-range laboratory test results at Week 12 will also be provided. Determination of clinical significance for all out-of-range laboratory values will be made by each investigator and included in the listing. In addition, a listing of all clinically significant laboratory test results will be provided.

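### The safety population requires a post-baseline evaluation that ITT does not, and Section 12.2.1 does not say which population the adverse event tables use

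*Combined protocol and SAP*

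**What the plan says.** The references are to the Amendment 3 protocol.

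- **ITT (Section 12.8.1):** "The ITT population will consist of all randomized subjects who received study medication". There is no follow-up condition.
- **Safety population (Section 12.8.1, stated twice):** "randomized subjects who are presumed to have used the study medication at least once and who provide at least one post-baseline evaluation".
- **Synopsis, Populations Analyzed:** the same condition, "presumed to have used the study medication at least once and who provide at least one post-baseline evaluation".
- **Synopsis, Safety Evaluation:** "All subjects who receive medication and provide at least one post-baseline evaluation will constitute the safety population". The AE tabulations are described directly after this sentence.
- **Section 12.2.1:** "All reported treatment-emergent AEs (TEAEs) will be summarized by the number of Subjects reporting AEs"; "TEAEs are those AEs with an onset on or after the date of the first study drug application"; and "The Fisher's Exact test will be used to compare the proportion of subjects in each treatment group who report any adverse event". Neither Section 12.2 nor Section 12.2.1 names an analysis population.

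No section defines what counts as a post-baseline evaluation.

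**The concern.** A safety set is meant to describe everyone exposed. This one is narrower than the ITT set, and membership depends on what happens after dosing. Section 5 lists irritation-type side effects of topical tretinoin, and the vehicle contains none. Early loss that differs by arm is therefore plausible, although nothing in the documents shows that it will occur.

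The second difficulty is that the AE denominator is not assigned. If the Synopsis governs and the tables use the safety population, a never-reassessed subject leaves both numerator and denominator. A recorded TEAE can then appear in a listing but not in the incidence table. If Section 12.2.1 is taken literally, that TEAE is summarized for a subject who is not in the safety set, and the denominator is undefined. The choice affects the incidence tables, the Fisher's exact comparison, and the rule that system organ classes and preferred terms are analyzed when at least 1% of subjects in any arm report them.

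**Working it through.** **Can the excluded group exist?**

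1. Section 11.1.2 has the first application made at the site at Baseline (Day 0), with the next visit at Week 4 (Day 28 ± 3). Section 11.3 ties safety assessments to Baseline and later visits.
2. Early-termination assessments are not guaranteed. Section 11.1.3 says they must be done, but Sections 7.1 and 8.3 say only that subjects will be asked, with qualifiers. Section 8.3 also provides for loss to follow-up.

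**Can such a subject have a recorded TEAE?**

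3. Section 11.4.2: "All AEs, whether in response to a query, observed by the study site personnel, or reported spontaneously by the subject, will be recorded". No visit is needed.
4. Section 8.3 puts discontinuation reasons on the final CRF and, where needed, the AE form. Section 11.4.6 requires reporting of SAEs the investigator learns of that occur within 30 days after stopping drug.
5. Section 12.2.1 counts TEAEs from the first application.

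Both answers are yes.

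**Arithmetic if the AE tables use the safety population.** The planned size, n = 400 per arm, is from Section 12.8.1. The documents give no AE incidence and no early-loss rate, so every rate below is an assumption. With x subjects having a TEAE among n dosed, and e excluded of whom a have a TEAE, the reported rate is (x − a)/(n − e). It falls below x/n when a/e exceeds x/n, rises when a/e is smaller, and is unchanged when they are equal.

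| Assumed incidence (x/400) | e=1, a=1 | e=1, a=0 | e=8, a=2 | e=8, a=0 |
|---|---|---|---|---|
| 5% (20) | 19/399 = 4.762% (−0.238) | 20/399 = 5.013% (+0.013) | 18/392 = 4.592% (−0.408) | 20/392 = 5.102% (+0.102) |
| 20% (80) | 79/399 = 19.799% (−0.201) | 80/399 = 20.050% (+0.050) | 78/392 = 19.898% (−0.102) | 80/392 = 20.408% (+0.408) |
| 40% (160) | 159/399 = 39.850% (−0.150) | 160/399 = 40.100% (+0.100) | 158/392 = 40.306% (+0.306) | 160/392 = 40.816% (+0.816) |

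Changes in parentheses are percentage points.

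**Varying the number excluded.** Suppose 80 subjects with an AE among those assessed, and 1%, 2.5% or 5% of 400 excluded (4, 10 or 20 subjects). The safety-population rate is 80/396 = 20.2%, 80/390 = 20.5% or 80/380 = 21.1%. Over all 400 dosed it is 80/400 = 20.0% if no excluded subject had an AE. If every one did, it is 84/400 = 21.0%, 90/400 = 22.5% or 100/400 = 25.0%. These are arithmetic bounds and say nothing about likely size.

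**The 1% threshold.** A term reported by 4/400 = 1.00% qualifies. If one of those four subjects is excluded it becomes 3/399 = 0.75%, and the term drops out unless the other arm reaches 1%.

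**The case against.** The strongest reply is that the harmful case is nearly empty. Because evaluation is undefined, a post-dose AE report graded for severity, seriousness and causality could itself count as one. Every subject with a recorded TEAE would then be in the safety set, and dropping the rest would only raise the rate slightly. Contacts before Week 4 are also planned: a Week 2 telephone reminder, and two calls and a certified letter before a subject is declared lost. AEs are listed by subject, SAEs are tabulated, and disposition is reported with reasons, so nothing disappears from the record. The separate SAP announced in Section 12 is not in the text reviewed and may assign the denominator. The Synopsis already points to the safety population. Finally, the condition is stated consistently, so preferring an all-dosed set is partly a matter of choice.

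Much of this stands as a limit on size. It does not remove the problem. The broad reading of evaluation is possible but is nowhere stated. A telephone contact can bring an AE to light without any protocol assessment being done. Listings give no incidence and no comparison between arms. If the Synopsis settles the population, the commitment in Section 12.2.1 to summarize all reported TEAEs can fail. If it does not, the AE denominator has no definition. Defining evaluation to include any post-dose safety contact would keep recorded TEAEs in the tables, but the denominator would still depend on follow-up after dosing.

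**Conclusion.** The concern holds. The safety population carries a post-randomization condition that ITT lacks. On the plain reading, a dosed subject never assessed again falls outside it, and Section 12.2.1 leaves the AE population unnamed. The effect is probably small, and its direction cannot be determined from the documents. In the scenarios tabulated above, the shift in an arm's incidence runs from −0.41 to +0.82 percentage points. Those figures rest on assumed incidences, assumed exclusions, and use of the safety population for the AE tables. No claim is made about the significance of the Fisher's exact test, and the efficacy testing in Section 12.1.5 does not depend on this point. The change should be made: it removes an avoidable source of bias from the safety comparison. Confidence is medium, because evaluation is undefined and the separate SAP may already settle the population.

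**What to change.** - Define the safety population as all randomized subjects who used study medication at least once. Remove the post-baseline-evaluation condition from both sentences in Section 12.8.1 and from the two Synopsis passages (Populations Analyzed and Safety Evaluation). Use one exposure wording throughout, since the Synopsis varies between presumed use and receipt.
- State in Section 12.2.1 that the AE tables, the Fisher's exact test and the 1% threshold use this population. The commitment to summarize all reported TEAEs then holds as written.
- Restrict only visit-based summaries (cutaneous scores, vital signs, laboratory values) to subjects with data at that visit.
- Carry the same definition into the SAP before unblinding.

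The cost is wording only, with no extra data collection. Never-assessed subjects without a recorded AE will dilute AE rates slightly. The per-protocol set is unaffected, because subjects who missed both Week 4 and Week 8 are already excluded from it.
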